7.4 Analysis of Secondary Objective

For the following measures, the frequencies and the percentages with corresponding exact 95% confidence intervals of participants will be tabulated by intervention group (if available), , study site and overall in the following measures.

7.4.1 Assessment of Subject Acceptability/Feasibility:

In the Eligible Population:

- those who refuse to participate in the study. The reasons of not interested in participating in the study will be summarized.

- For those who prefer to see an allergist for skin testing, summarize the reasons why they have not seen an allergist until now.

In the Treated Population:

- those who experience elicited reactivity to PCN allergy skin testing in the PST Group and oral challenge by dosage and group.
- those who find the testing procedures of to be helpful. The reasons of finding the PCN testing not helpful will be summarized.
- Those feeling comfortable with allergy testing conducted in settings where STD services are provided rather than by an allergist.
- chance of referring a friend or family member having a history of penicillin allergy.
- confidence in taking PCN or similar antibiotics among those who have been skin tested and are negative for PCN allergy.

7.4.2 Assessment of Provider Acceptability/Feasibility:

In the Provider Population, summarize by group (if possible) in numbers and proportion of:

- those who prefer PCN skin testing, direct oral challenge, or no preference.
- those who feel PCN allergy assessment can be performed safely and effectively in a setting which treats patients with STIs.
- those who will offer PCN allergy assessment in the future.
- reasons why study providers will not offer PCN allergy assessment in the future.

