We anticipate that screening, consenting, enrollment of subjects with a history of PCN (B-lactam) allergy and all study procedures will take place during one or two clinic visits. Study sites can also choose to do oral or electronic consents and complete initial screening assessments (including the Allergy History Questionnaire) by telephone. The length of the study visit will be about 1-3 hours in addition to the clinical appointment depending into which method of PCN allergy validation the participant is enrolled. All participants will be screened for study interest and eligibility. Once participants have given their written, oral, or electronic consent and been enrolled, study staff will administer the PCN (B-lactam) allergy history screening questionnaire. All participants who complete the skin testing and/or oral challenge will be asked to complete an acceptability survey on the PCN testing procedures at the end of the study visit. See the table below for the anticipated length of time the study visit will take for both the PST and the DOC Groups.

Study Procedures	Anticipated Length of Time
PST Group	

 Screening, informed consent, enrollment Allergy history screening questionnaire* Skin testing (if qualified to receive) Oral challenge observation (if qualified to receive) Acceptability survey on the PCN testing procedures 	30 minutes 30 minutes 30-60 minutes 60 minutes 10 minutes
TOTAL	1 to 3½ hours
DOC group	

 Screening, informed consent, enrollment Allergy history screening questionnaire* Oral challenge 1st step observation (if qualified to receive) Oral challenge 2nd step observation (if qualified to receive) Acceptability survey on the PCN testing procedures 	30 minutes 30 minutes 30 minutes 30 minutes 10 minutes
TOTAL	1 – 2¼ hours

* If subjects have a higher-risk history of allergy based on responses to the questionnaire, their study participation will be complete after 1 hour.

If enrolled subjects cannot complete all study procedures for which they are qualified during the clinic visit, study staff will give them the option to return at a later date (within six weeks from the

screening visit) to complete the skin testing and/or oral challenge and subject acceptability survey.

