6.1.2.2 Procedures After Defining Risk Category

Subjects classified with a low-risk history will progress to either skin testing (PST Group) or direct oral challenge (DOC Group), depending on which method of validating PCN allergy they are assigned. Subjects who meet the higher-risk classification will be advised that further elucidation of their allergy status will require a formal allergy evaluation. Referral resources will be provided.

All participants classified as low-risk and who meet additional qualification criteria to receive allergy testing (See Sec 6.1.3) will undergo the following procedures:

ASSIGNED TO PST GROUP

- Administration of skin test (prick test first and, if indicated, intradermal test)
- If skin test results are negative, option to receive oral challenge of 250 mg of amoxicillin
- Pre-oral challenge brief PE, assessment of vital signs and measurement of peak flow
- Administration of oral challenge
- Post-oral challenge brief PE, vital sign assessment and peak flow measurement

ASSIGNED TO DOC GROUP

- Pre-oral challenge brief PE, assessment of vital signs and measurement of peak flow
- Administration of oral challenge (first step) of 25 mg of amoxicillin, vital sign assessment and, if indicated, administration of oral challenge (second step) of 250 mg of amoxicillin
- Post-oral challenge brief PE, vital sign assessment and peak flow measurement

All participants will undergo the following procedures after allergy validation methods are offered or completed:

- Administration of subject acceptability survey on PCN testing procedures for all subjects who were offered skin testing (with or without oral challenge) or direct oral challenge
- Written documentation of PCN allergy testing results for all subjects who received skin testing (with or without oral challenge) or direct oral challenge to share with subject's medical care providers

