6.2 PCN Skin Testing

Depending on the outcome of the PCN (B-lactam) allergy history screening questionnaire, participants may qualify to receive the PCN skin test.

- Participants with a higher risk of PCN allergy will not proceed to the PCN skin test or oral challenge. Their study participation will be complete. Subjects will be provided with a written referral to local allergy providers.
- Participants with a low risk of PCN allergy and assigned to the PST intervention group will be offered the PCN skin test.

Staff will verify that qualified participants do not meet any additional criteria that would preclude them from skin testing using the Skin Test Qualification Checklist. Study staff will explain the skin testing procedures to participants who may decide to accept or decline skin testing. If they decline, they will be asked to complete the subject acceptability survey and their study participation will be complete. Staff will note the reason(s) they declined to be skin tested on the appropriate CRF.

Study staff will perform the allergy skin testing for PCN allergy in accordance with standard allergy testing procedures and instructions provided in the PRE-PEN® kit package insert.³¹ Prick (Puncture) tests will be performed before proceeding to intradermal testing. Prick testing is performed at marked sites on the inner volar aspect of the forearm. Testing for controls and each reagent is performed singly.

Reagents and controls for prick and intradermal tests include:

1. Controls:
 - a.) Negative Control: Sodium chloride solution without preservative

* e.g., patients presenting with secondary syphilis

- b.) Positive Control: Histamine:
 - i. Prick testing: histamine base 1 mg/ml
 - ii. Intradermal testing: histamine base 0.1 mg/ml
2. Reagents:
 - a.) PRE-PEN® (major determinant)
 - b.) Penicillin G 10,000 U/ml (minor determinant)

Intradermal testing will not be performed if there is a positive or uninterpretable reaction to PRE-PEN® and/or Penicillin G during the prick test. If the prick skin test results are negative the participant is qualified for intradermal testing. Study staff will perform duplicate intradermal skin testing of each reagent and single intradermal skin testing of the positive and negative controls on the inner volar aspect of the forearm. The same arm will be used for both prick and intradermal testing.

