4.4 Treated Population

This population includes all enrolled participants who received Method 1 PST or Method 2 DOC. This analysis population will mainly be used for analyzing participants' baseline characteristics, primary outcome measures and secondary outcome measures.

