4.5 Per-Protocol Population

This population includes all treated participants who completed the study without protocol deviation. This analysis population will also be used for analyzing participants' baseline characteristics, primary outcome measures and secondary outcome measures.

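### SAP 7.4.1 confines the survey-based acceptability items to treated subjects, so survey answers from subjects who decline the skin test or the direct oral challenge have no planned analysis

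*SAP*

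**What the plan says.** **Analysis.** SAP 7.4.1 lists the survey items under a Treated Population heading, starting with "those who find the testing procedures of to be helpful" and the reasons given by those who do not. Comfort with testing in an STD setting, referral of a friend or relative, and confidence in taking penicillin follow under the same heading. SAP 4.4 defines that population: "This population includes all enrolled participants who received Method 1 PST or Method 2 DOC". The only other subject population that the SAP assigns to secondary outcomes in general is the Per-Protocol Population, a subset of it (SAP 4.5): "This population includes all treated participants who completed the study without protocol deviation".

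**Collection.** Protocol 6.1.2.2 sets a wider rule: "Administration of subject acceptability survey on PCN testing procedures for all subjects who were offered skin testing", with direct oral challenge included. Protocol 6.2 says of subjects offered the skin test: "If they decline, they will be asked to complete the subject acceptability survey and their study participation will be complete". Protocol 6.3 makes the same provision for those who decline the oral challenge in either group. Both sections have staff record the reason for declining on a CRF.

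**Conflicting text.** Protocol 4.1 is narrower: "All participants who complete the skin testing and/or oral challenge will be asked to complete an acceptability survey". Protocol 6.4 and the opening line of Appendix B Section 3 also time the survey after testing is completed.

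**The concern.** The secondary objective is acceptability of the testing algorithm, and Protocol 8.1.2 defines the helpfulness outcome on study subjects without limiting it to those tested. Protocol 6.1 also treats the time burden as a possible barrier and a key operational outcome. Low-risk subjects who enrol and then decline testing bear directly on these questions. Two survey items need no experience of testing: Q16 (comfort with testing outside an allergist's practice) and Q17 (willingness to refer others). Appendix B heads both as questions for all subjects. Reporting them only among people who accepted testing conditions the answer on acceptance. If decliners differ, the reported proportion does not describe the population to whom a clinic would offer the algorithm.

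**Working it through.** **Step 1: where each group of subjects appears in the SAP.**

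| Enrolled low-risk subject | Asked to complete the survey (Protocol) | In the Treated Population (SAP 4.4) | Where the SAP reports them |
|---|---|---|---|
| Received skin test or direct challenge | Yes | Yes | 7.4.1 survey tables |
| Declined skin test (PST) | Yes, 6.1.2.2 and 6.2 | No | 7.1 disposition count |
| Declined direct oral challenge (DOC) | Yes, 6.1.2.2 and 6.3 | No | 7.1 disposition count |
| Skin tested, then declined oral challenge (PST) | Yes, 6.1.2.2 and 6.3 | Not stated | 7.1 count; 7.4.1 unclear |

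The Eligible Population item in SAP 7.4.1 covers refusal to join the study. It does not cover refusal of testing after enrolment.

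The last row matters because SAP 7.4 tabulates by intervention group. A DOC subject who refuses amoxicillin has received nothing and leaves the Treated Population. A PST subject who refuses amoxicillin after a skin test may stay in. The same refusal could therefore be handled differently in the two groups.

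**Step 2: possible size.** The documents give no decline rate, expected proportion or precision target for acceptability, so there is no planned figure to reproduce. Let d be the proportion declining among those offered testing, and p_T and p_D the favourable proportions among treated subjects and decliners.

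- All offered: (1 − d) × p_T + d × p_D
- Excess of the treated-only figure: p_T − [(1 − d) × p_T + d × p_D] = d × (p_T − p_D)

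Assumptions: p_T = 90%; p_D = 60% or 30%; d = 5%, 10% or 20%.

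- d = 5%: 0.05 × 0.30 = 1.5 points; 0.05 × 0.60 = 3.0 points
- d = 10%: 0.10 × 0.30 = 3.0 points; 0.10 × 0.60 = 6.0 points
- d = 20%: 0.20 × 0.30 = 6.0 points; 0.20 × 0.60 = 12.0 points
- p_D = 90%: zero at every d

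**Step 3: comparison with the reported uncertainty.** Take 1,000 enrolled (SAP 1) less the 5% higher-risk share assumed in SAP 6: 1,000 × 0.95 = 950 offered testing. This ignores subjects ruled out under Protocol 6.1.3. Exact (Clopper-Pearson) 95% intervals, with counts rounded to whole subjects:

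| Declining | Treated / decliners | Treated only | All offered, p_D = 60% | All offered, p_D = 30% |
|---|---|---|---|---|
| 5% | 902 / 48 | 90.0% (87.9–91.9) | 88.5% (86.3–90.5) | 86.9% (84.6–89.0) |
| 10% | 855 / 95 | 90.1% (87.9–92.0) | 87.1% (84.7–89.1) | 84.0% (81.5–86.3) |
| 20% | 760 / 190 | 90.0% (87.6–92.0) | 84.0% (81.5–86.3) | 78.0% (75.2–80.6) |

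The treated-only interval has a half-width of about 2 points. Under these assumptions, the gap exceeds it at 10% declining or more.

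**The case against.** Several counter-arguments stand in part.

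- *Non-acceptance is already reported.* SAP 7.4.1 analyses refusal of the study, with reasons, in the Eligible Population, and SAP 7.1 and Protocol 8.3 count those who refuse skin testing and oral challenge. A reader might infer that acceptability as a whole is analysed only in treated subjects. The documents do not support that; the gap concerns the survey items.
- *Helpfulness presupposes testing.* The reasons offered in Q15 concern the length and discomfort of the tests, and Q18 concerns confidence after a negative result. Restricting Q14, Q15 and Q18 to treated subjects is a defensible choice of estimand.
- *It is uncertain that decliners will have survey data.* Protocol 4.1, 6.4 and Appendix B Section 3 tie the survey to completed testing. The SAP was also written for protocol version 2.0 and has a two-week return window (SAP 4.2) where Protocol 5.2.2 has six weeks, so part of the mismatch may reflect versions. That stands as a reason to reconcile the text. It does not remove the three sections that ask for, or provide for, the survey in subjects who do not go on to testing.
- *Few may decline.* Protocol 5.2.2 excludes people who can neither stay nor return, so refusals after enrolment may be uncommon. Their number is unknown.
- *The measures are descriptive.* They carry no hypothesis test or power target, and the NPV and prevalence analyses are unaffected.

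**Conclusion.** The mismatch between collection and analysis is in the text. It is certain for subjects who decline the skin test or the direct oral challenge, and undetermined for PST subjects who decline only the oral challenge. It affects descriptive secondary measures, chiefly Q16 and Q17.

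A reader might go further and conclude that the acceptability estimates are biased upward. The documents do not establish this. That decliners are less favourable is a reasonable inference, and the illustrative gaps above rest entirely on assumed decline and response rates. A reader might also multiply an assumed 90% by the acceptance rate, giving 0.90 × (1 − d) = 81%, 72% and 63% at 10%, 20% and 30% declining. As an estimate of attitudes, that supposes no decliner answers favourably, an extreme case for which the documents give no basis. Tabulating the decliners' answers would show whether there is a difference.

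**What to change.** - In SAP 7.4.1, define an offered-testing population: low-risk enrolled subjects who were offered skin testing or direct oral challenge.
- Report Q16 and Q17 in that population by group and overall, with exact intervals. Show decliners separately as well, alongside their recorded reasons for declining.
- Keep Q14, Q15 and Q18 in the Treated Population, and print the acceptance rate beside them.
- In SAP 4.4, state whether PST subjects who were skin tested but declined the oral challenge count as treated.
- Reconcile Protocol 4.1, 6.4 and the Appendix B Section 3 heading with 6.1.2.2, 6.2 and 6.3 on who completes the survey, and check the SAP against the current protocol version on this point.

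The cost is one more table, from data the protocol already provides for, a few lines of clarification, and possibly less favourable proportions for Q16 and Q17.

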6.4 Study Completion and Documentation of Allergy Testing Results

After the skin testing and/or oral challenge is completed, the participants will be asked to complete the subject acceptability survey to get their opinion of the PCN testing procedures conducted during the study, their results, and the subject's confidence that they will be able to take PCN (B-lactam) drugs in the future.

The subjects will be provided written documentation of the PCN (B-lactam) allergy testing procedures performed including a description of the skin testing and oral challenge, and verification of their PCN allergy test results (negative, positive or referral to allergist for further testing), which they will be encouraged to share with their medical providers.

In addition, we will provide the local STD clinic with the results, and these can be inserted into the medical record, as appropriate.

Subjects who have higher-risk histories which preclude skin testing and direct oral challenge or have ambiguous or uninterpretable results will be provided with a referral to local allergy providers. Each research site will maintain a list of local allergy providers for referral.

There are no follow up visits required. Subjects will be given instructions to contact study staff in the unlikely event of complications.

Incentives for a participant's time, transportation, and other expenses will be provided according to local IRB approval. Study staff will provide incentives depending on what procedures from the study visit the participant completed.

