8.4.2 Analysis of Secondary Endpoints

The frequency and the percentage of participants 1) who experienced elicited reactivity to PCN allergy skin testing in the PST Group and oral challenge in both groups; 2) who refused to participate the study; 3) who found the testing procedures of no value will be tabulated by study site. The proportions of participants 1) experiencing elicited reactivity to penicillin allergy testing; 2) reporting reasons for refusing to participate in the study or finding the testing procedures to be of no value; 3) describing confidence in taking PCN or similar antibiotics among those who were negative on oral challenge will be calculated with corresponding exact 95% confidence intervals.

The same approach will also be used to evaluate the feasibility of providers who will offer the PCN allergy assessment in the future and the reasons among those providers who will not offer the PCN allergy assessment in the future. The evaluation of the secondary endpoints will be conducted by intervention group and overall

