 - f. Other (please list) _____
 - g. None – I have not taken any of these medications

(If Yes to a, b, c, d or e, exclude from skin test)

Section 3: Subject Acceptability Survey**Questions to ask after skin testing and oral challenge procedures are completed**

FOR ALL SUBJECTS

14) Did you find the penicillin testing procedures to be helpful?

(Scale of 1-5, where 1 is extremely helpful, 5 is not helpful at all)

(if 4 or 5, go to Q15; otherwise skip to Q16)

15) Why were the penicillin testing procedures not helpful?

- a. Took too long
- b. Testing was uncomfortable
- c. Other (Please list) _____

16) Were you comfortable with allergy testing conducted in settings where STD services are provided rather than by an allergist?

(Scale of 1-5, where 1 is extremely comfortable, 5 is not comfortable at all)

17) If a friend or family member had a history of penicillin allergy, would you refer them for testing?

(Scale of 1-5 where 1 is definitely yes, 5 is definitely no)

FOR SUBJECTS WHO HAVE BEEN SKIN TESTED AND ARE NEGATIVE FOR PCN ALLERGY

18) How confident are you that you can now take penicillin or similar antibiotics?

(Scale of 1-5 where 1 is very confident and 5 is not confident at all)

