3.2 Secondary Outcome measures

- Acceptability
 - Proportion of study subjects who find the testing procedures to be helpful.
 - Reasons why study subjects refuse to participate in the study.
 - Proportion of study subjects who were negative on oral challenge who now feel confident in taking PCN or similar antibiotics.
 - Proportion of study providers who will not offer PCN allergy assessment in the future.
- Feasibility
 - Proportion of study providers who will offer PCN allergy assessment in the future.
 - Reasons why study providers will not offer PCN allergy assessment in the future.
- Both acceptability and feasibility
 - Types and frequencies of elicited reactivity to PCN through skin testing and oral challenge among study subjects.

4. Analysis Populations

This analysis plan describes six different analysis populations that are used for different purposes. The final statistical report will include an accounting of all eligible persons screened and the number enrolled. The reason for excluding any data from any analysis population will be documented.

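### SAP 7.4.1 and the heading over Q18 restrict the confidence outcome to skin-tested negatives, which leaves the DOC group with no estimate

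*SAP*

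**What the plan says.** SAP 3.2 lists the outcome as "Proportion of study subjects who were negative on oral challenge who now feel confident in taking PCN or similar antibiotics". Protocol 3.2.2 and 8.1.2 define it identically. Protocol 8.4.2 plans the proportion "describing confidence in taking PCN or similar antibiotics among those who were negative on oral challenge" and adds: "The evaluation of the secondary endpoints will be conducted by intervention group and overall".

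SAP 7.4.1 places the measure under the Treated Population, which SAP 4.4 describes as "all enrolled participants who received Method 1 PST or Method 2 DOC". The bullet itself, however, reads "confidence in taking PCN or similar antibiotics among those who have been skin tested and are negative for PCN allergy". SAP 7.4 says results will be "tabulated by intervention group (if available").

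In Section 3 of Protocol Appendix B, Q14 to Q17 are headed as being for all subjects. Q18, on confidence, stands under a separate heading: "FOR SUBJECTS WHO HAVE BEEN SKIN TESTED AND ARE NEGATIVE FOR PCN ALLERGY".

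Protocol 6.4 is broader: "After the skin testing and/or oral challenge is completed, the participants will be asked to complete the subject acceptability survey", and it names confidence in taking these drugs as part of that survey. Protocol 6.1.2.2 likewise gives the survey to everyone offered either form of testing.

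**The concern.** DOC subjects go straight to the two-step challenge, so a denominator of skin-tested subjects contains none of them. The secondary objectives cover skin testing followed by challenge as well as direct challenge. Whether people cleared without a skin test trust the result is the DOC half of this outcome.

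The gap could pass unnoticed. SAP 7.4 makes the split by group conditional on availability, so an empty DOC column would need no explanation, and a PST-only figure could be printed as the overall result. If a form built from Appendix B skips Q18 for DOC, the answer is missed at the visit, and Protocol 6.4 requires no follow-up visit at which to ask again.

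**Working it through.** The plan gives no sample size or precision figure for this outcome, so there is nothing to reproduce. The check compares the texts and then counts who is affected.

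**Step 1: who is in the set**

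| Place | Set described | DOC in it? |
|---|---|---|
| Protocol 3.2.2, 8.1.2; SAP 3.2 | Negative on oral challenge | Yes |
| Protocol 8.4.2 | Same set, by group and overall | Yes |
| Protocol 6.4 | Asked after either form of testing | Yes |
| SAP 7.4.1 | Treated, skin tested and negative | No |
| Appendix B, heading over Q18 | Skin tested and negative | No |

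The SAP therefore conflicts with itself (3.2 against 7.4.1) as well as with the protocol.

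**Step 2: the set also differs within PST.** Under Protocol 6.3, a skin-test negative who declines the challenge still completes the survey. Protocol 5.3 describes only the questionnaire and skin testing for pregnant women, all of whom are placed in PST. Both kinds of subject meet the SAP 7.4.1 wording, yet neither is negative on oral challenge. The documents give no rate for either, so I do not estimate one.

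**Step 3: DOC subjects omitted.** Inputs:
- 100 DOC subjects per site (Protocol 4.1, SAP 1).
- Five sites (SAP 1) or four (Protocol Summary).
- 5% higher-risk and not tested, and allergy of 1%, 3% or 5% (Protocol 8.2, SAP 6).

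Formula: sites × 100 × 0.95 × (1 − allergy).

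- Five sites: 500 × 0.95 = 475. Then 475 × 0.99, 0.97, 0.95 = 470, 461, 451.
- Four sites: 400 × 0.95 = 380. Then 380 × 0.99, 0.97, 0.95 = 376, 369, 361.

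If the planned numbers are already net of higher-risk subjects, the 5% is not deducted and the counts are 495, 485, 475 (five sites) or 396, 388, 380 (four). All are before refusals and failed qualification.

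**Step 4: share of the intended set.** With equal groups and the same losses in each, DOC is one half. PST loses some subjects before challenge, so its share is somewhat smaller. Applying the plan's 95% specificity to the skin test, with 3% allergy and five sites, PST challenge-negatives are about 475 × 0.97 × 0.95 = 438. DOC is then 461 / (461 + 438) = 51%.

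**Step 5: precision, as an illustration.** Take 3% reacting, five sites and no higher-risk deduction: 485 per group, 970 together. The true proportion confident is not given, so I assume a range. Exact 95% half-widths, in percentage points:

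| Assumed proportion confident | n = 485 | n = 970 |
|---|---|---|
| 50% | 4.5 | 3.2 |
| 80% | 3.7 | 2.6 |
| 90% | 2.8 | 1.9 |

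The loss of precision is modest. The real loss is that one group has no estimate.

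**The case against.** The strongest reply is that loss of DOC data is not shown. Protocol 6.1.2.2 and 6.4 give DOC subjects the survey, and 6.4 includes confidence in it. Protocol 8.4 says changes to the summary plan will be documented in the SAP, and none is documented here. The SAP bullet closely follows the Q18 heading, so it looks like carried-over wording. No programmed skip for Q18 is described, and SAP 1 leaves the table shells to a later version. Contact details are collected at enrolment (Protocol 6.1.2), so a single rating could be obtained without a visit.

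Much of this stands. Non-collection is possible but not established, and a missed answer might be recoverable. None of it puts DOC subjects back into the SAP 7.4.1 denominator: even if every DOC subject answers Q18, the analysis as worded leaves those answers out. If the wording was merely carried over, that is a reason to correct it.

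Two objections to the numbers are also fair. DOC is not exactly half of the intended set, and the 5% deduction is one reading of the plan. Steps 3 and 4 show both, and neither changes the conclusion.

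**Conclusion.** The concern holds. SAP 7.4.1 and the Q18 heading contradict the declared outcome. Applied literally, they give a DOC denominator of zero, an overall figure that is PST only, and a PST set that may include subjects never challenged. Roughly half of the intended subjects are omitted, about 360 to 495 depending on the number of sites, the allergy rate and whether higher-risk subjects are deducted. These counts assume full enrolment at 100 per group per site and no refusals.

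The contradiction in the text is certain; actual loss of DOC answers is conditional on the form and table shells. The scope is one item of one acceptability outcome. The NPV and prevalence analyses and the sample size are untouched. It should be corrected, but it does not threaten the trial's main conclusions.

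**What to change.** - **Appendix B:** reword the heading over Q18, and any matching form logic, so that the item is asked of every tested subject with a negative result in either group.
- **SAP 7.4.1:** set the denominator to subjects negative on oral challenge, PST or DOC, and report by group and overall. Do not let the availability proviso in SAP 7.4 apply to this outcome.
- **Separate line:** list PST skin-test negatives who were not challenged on their own, outside the outcome.
- **If enrolment has started:** check whether Q18 has been asked in DOC, and state the number of missing answers by group.

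A separate, minor edit belongs in the same revision. The parenthesis in SAP 7.5 assigns the test dose to DOC and both test and full dose to PST. Protocol 6.3.1, 6.3.2 and Appendix A and SAP 1 describe one step in PST and two in DOC. These passages must be reconciled so that the tables match what each group receives. Only the vital-sign and examination tables are affected; reactions, reactivity by dosage and adverse events are reported regardless.

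The cost is SAP wording, one heading in a protocol appendix and the corresponding form logic. No visit, procedure or subject is added.
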